## Flow Chart :

#### **4.2 Number of Patients**

Number of Patients The planned enrollment for this trial includes 60 stroke patients, with an overall evaluable sample size of 70 individuals. This estimation is based on the recommendation by Lewis and Sauro (2009), who suggest that a minimum of 12 participants is appropriate for usability assessments. In the present study, participants will be categorized into four subgroups based on MAS scores (either <1 or ≥1) and intervention type (experimental or control). To ensure that each subgroup has at least 12 participants, a minimum of 48 participants is required (12 per subgroup). An additional 25% (12 participants) will be recruited to account for potential dropout, bringing the total number of stroke patients to be enrolled to 60. Our center has the capacity to recruit and evaluate all 70 participants. In addition to prospective participants, retrospective data from 60 stroke patients will be included for analysis. Furthermore, a total of 10 individuals—including trained therapists and healthy subjects (such as caregivers or family members who have received prior instruction)—will be included to assess usability and support the study's broader evaluation framework.

framework.

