# 4. Study Design

## 4.1 Overall Design

The study employs a novel non-powered bi-manual rehabilitation device based on mechanical transmission principles, specifically designed for upper limb training in post-stroke

patients. The device operates through a linear guide rail system that enables the unaffected limb to drive the movement of the affected limb along a mirrored trajectory. This bilateral training approach allows simultaneous motion of both upper limbs, enabling the unaffected side to assist in generating active movement in the hemiplegic arm.

Key features of the device include: (1) bilateral limb synchronization, whereby movement of the unaffected upper limb facilitates motion of the affected limb; (2) a purely mechanical, power-free transmission system utilizing linear rail sliders; and (3) training guided along specific two-dimensional movement trajectories. The device is expected to maintain or improve joint range of motion (ROM), reduce spasticity as measured by the Modified Ashworth Scale (MAS), and promote neuroplasticity in the affected neural pathways.

The structural design centers around a central transmission module that links the motion of the two limbs via linear rails to minimize mechanical resistance. The forearm is secured using an end-effector mechanism, and the device allows for directional movement through longitudinal and lateral rail systems. Different training trajectories can be achieved by varying the patient's seated position, supporting functional training across a range of upper limb motion patterns.

Prior to training, the rehabilitation physician evaluates the affected shoulder and elbow joints using the Brunnstrom Recovery Stage, Fugl-Meyer Assessment for Upper Extremities (FMA-UE), and MAS. Based on MAS scores, patients are stratified into two groups: those with MAS <1 and those with MAS  $\geq$ 1. Participants are then randomly assigned to either the experimental group—receiving bilateral upper limb training with the device combined with conventional occupational therapy—or the control group—receiving only conventional upper limb occupational therapy.

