## 10. Criteria for the termination of the trial

(1) Enroll requested number of patients and complete the study(2) Relevant research has been published and could confirmed the hypothesis of this study

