# 11. Statistical Considerations

## **11.1 Sample size Determination**

Based on the recommendations by Lewis and Sauro (2009), a minimum of 12 participants per group is considered appropriate for usability testing. In this study, participants will be categorized into four subgroups based on muscle tone classification (MAS < 1 or MAS  $\geq$  1) and treatment allocation (experimental or control group), resulting in a minimum required sample size of 48 (12 participants per subgroup). To account for an anticipated dropout rate of approximately 25%, an additional 12 participants will be recruited, leading to a total target enrollment of 60 stroke patients. In addition, 10 trained healthy participants—including caregivers or family members—will be included for usability assessments and device operation training. The total number of evaluable subjects for the study will therefore be 70.

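### The sample size does not ensure 12 patients in each MAS-by-arm subgroup: it assumes equal MAS strata, and the readable text neither states nor secures that.

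*Combined protocol and SAP*

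**What the plan says.** Section 4.2 explains that "participants will be categorized into four subgroups based on MAS scores" (below 1, or 1 and above) and by treatment arm. It continues: "To ensure that each subgroup has at least 12 participants, a minimum of 48 participants is required (12 per subgroup"). Section 11.1 gives the same derivation, "resulting in a minimum required sample size of 48 (12 participants per subgroup"), and the synopsis repeats it. The increase to 60 is assigned to losses: "An additional 25% (12 participants) will be recruited to account for potential dropout", "bringing the total number of stroke patients to be enrolled to 60". No power, effect size or standard deviation is given, so 12 per cell is the only stated basis for the size.

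On stratification, section 4.1 says "patients are stratified into two groups: those with MAS <1 and those with MAS" of 1 or more, after which patients are randomised. The only MAS limit on entry (5.1, repeated in 11.3) is a score below 3, so both strata are open. Section 10 ends the trial on the condition "Enroll requested number of patients and complete the study" and does not mention strata. Incomplete cases are left out of the analysis (synopsis, 11.4). Section 11.2 plans a one-way ANOVA across the subgroups.

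**The concern.** MAS is a baseline characteristic that patients bring with them. Randomising within MAS strata can balance the arms inside each stratum, but it cannot fix how many patients each stratum holds. A promise about all four cells therefore needs either a rule on stratum sizes or a stated assumption about the MAS mix. The readable text has neither.

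At stake is the number on which the trial's size rests. If the mix is uneven, the two cells of the scarcer stratum fall below the plan's own minimum while the other two are over-filled, and the subgroup comparison in 11.2 is thin where the plan says it will not be. The problem arises even with no dropout, so it is separate from how the dropout allowance was calculated.

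**Working it through.** **Inputs from the documents.** Minimum of 12 per cell and four cells (4.2, 11.1); 60 patients enrolled, of whom 12 are the dropout allowance (4.2, 11.1); complete-case analysis (synopsis, 11.4).

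**Assumptions.** Allocation is 1:1 within strata; the ratio is not stated, but equal cells imply it. The smaller stratum's share of eligible patients, p, is not given, so a range is shown.

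**Step 1: the plan's figure.** 4 x 12 = 48 and 48 x 1.25 = 60. Both reproduce. The 12 extra patients are 12/60 = 20% of those enrolled.

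**Step 2: the split that the plan needs.** The smaller stratum must supply 2 x 12 = 24 patients.
- From 48 patients: 24/48 = 50%.
- From 60 enrolled, no losses: 24/60 = 40%. Any realised split from 24:36 to 36:24 is enough.
- From 60 enrolled after 20% loss: 24/(60 x 0.80) = 50%, which leaves no slack.
- From 60 enrolled after 25% loss: 24/(60 x 0.75) = 53%, which a smaller stratum cannot be. Equal strata then average 60 x 0.5 x 0.5 x 0.75 = 11.25 per cell.

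**Step 3: expected size of the smaller cells.** Enrolled: 60 x p x 0.5. After 12 losses: multiply by 0.80.

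**Step 4: chance that all four cells reach 12.** With no dropout this is the exact binomial probability that one stratum holds 24 to 36 of the 60: the sum over x = 24 to 36 of C(60, x) p^x (1 - p)^(60 - x). With dropout it is a simulation of 400,000 trials, each patient lost independently with probability 0.20.

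| p | Smaller cell, enrolled | Smaller cell, after 12 losses | All four at 12 or more, no dropout | All four at 12 or more, 20% dropout |
|---|---|---|---|---|
| 50% | 15.0 | 12.0 | 91% | 9% |
| 45% | 13.5 | 10.8 | 81% | 7% |
| 40% | 12.0 | 9.6 | 55% | 4% |
| 30% | 9.0 | 7.2 | 6% | 0.2% |

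**Step 5: what a stratum target would achieve.** With 30 per stratum there are 15 per cell. At 20% random dropout one cell keeps at least 12 with probability 0.648, and all four do with probability 0.648^4, about 18%. At 25% dropout the chance for all four is about 5%.

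**The case against.** Several points on the other side are fair.

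- **The flow chart is not shown.** The contents list places it under 4.1, and it could carry numbers per stratum. The finding is therefore limited to the readable text. If the chart does hold stratum targets, they belong in 4.2 and 11.1 as well.
- **A reader might infer that the promise fails unless MAS splits almost evenly.** The documents do not support that. At enrolment any split between 40:60 and 60:40 meets 12 in every cell, and nothing in the plan says that the real mix lies outside that band. The low chances at p = 30% depend on an assumed share.
- **A reader might infer that the site will stop at 60 whatever the mix.** Section 10 speaks of the requested number and does not say that this is only the total. The supportable statement is that the plan does not say how the per-subgroup minimum is secured.
- **The consequence is limited.** The figure of 12 comes from a usability-testing recommendation and is not a power calculation. The primary endpoint is FMA-UE, and the stratum mix does not change the arm totals in its t-test. ANOVA does not need equal cells: for a contrast between strata, a 30:70 mix keeps 4 x 0.3 x 0.7 = 84% of the information of an equal split.

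Two other defences do not hold. The extra 12 patients cannot be counted on to absorb imbalance, because 4.2 and 11.1 assign them to dropout. The retrospective data from 60 patients in 4.2 are not assigned to MAS-by-arm cells, and the plan does not say that any of those patients were randomised or used the device.

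**Conclusion.** The point holds in limited form. Twelve per subgroup is not ensured by the design as written. It is an expected size, and it is reached only if the MAS strata are equal and losses do not exceed the 12 allowed for. Before dropout, the chance that all four cells reach 12 runs from 91% to 6% as the smaller stratum's share goes from 50% to 30%. With 20% random dropout it is about 9% at best. These figures rest on 1:1 allocation within strata, independent dropout and an assumed range for the MAS mix.

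The results do not show that the trial will miss its subgroup sizes, that the primary comparison is harmed, or that a stratum cap would restore the guarantee. What needs correcting is a stated property of the sample size that the plan does not secure.

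**What to change.** In the synopsis, 4.2 and 11.1, replace the statement that each subgroup is ensured at least 12 with wording such as: *an expected 12 per subgroup after 12 losses, assuming equal MAS strata*. Add the expected size of the smaller cells under uneven mixes: 9.6 at 40:60 and 7.2 at 30:70. This is a text change with no extra patients and no change in conduct.

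Optionally, set a target of 30 patients per MAS stratum (15 per arm) within the total of 60, and close a stratum when it is full. State with it that:

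- it removes only the stratum imbalance, and all four cells keep 12 completers with a chance of about 18% at 20% dropout;
- it may slow accrual in the one-year study period. If the scarcer stratum were 30% of eligible patients, filling it would take about 30/0.30 = 100 eligible patients, so about 100 - 60 = 40 would be turned away.

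Whether that trade is worthwhile depends on the site's MAS mix, which the sponsor may know and should state.

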## 4.3 Schedule of Activities

# Time-Event scheme:

Phase	Recruitment	Pre-treatment	Allocation	Rehabilitation	Post-treatment
		Assessment		programs	Assessment
Evaluation					
Rehabilitation ward /	V				
Outpatient department					
Screening /Administration					
Inclusion / Exclusion criteria	V	V			
Patient profile	V	V			
Assessment					
Brunnstrom stage		V			V
Fugl-Meyer Assessment-Upper		V			V
Extremities (FMA-UE)					
Modified Ashworth scale (MAS)		V			V
Questionnaire					
System Usability Scale (SUS)					V
questionnaire					
Satisfaction questionnaire					V

# 5. Study Population

#### 5.1 Inclusion Criteria

- Stroke onset  $\leq 12$  months
- Age 18–70 years
- Stable physiological and neurological status for  $\geq$ 72 hours
- Able to follow at least two-step commands
- Written informed consent obtained
- Unilateral upper limb hemiplegia
- Brunnstrom stage > I (proximal UE)
- MAS < 3 (affected UE)

## 5.2 Exclusion Criteria

- Musculoskeletal impairments preventing device use
- Active, non-healed dermatological lesions

## 5.3 Withdrawal criteria

Participants will be withdrawn from the study if they (1) become lost to follow-up, (2) develop new central nervous system lesions, or (3) experience decompensated systemic diseases that may compromise safety or study participation.

## 6. Treatments

## 6.1.Treatment Administration

This study utilizes a non-powered bi-manual mechanical device for upper limb rehabilitation in post-stroke patients. The device operates via a linear rail transmission system that allows movements initiated by the unaffected upper limb to be mechanically transmitted to the affected limb, thereby facilitating bilateral synchronous motion along a defined trajectory within a single plane. This design enables joint mobilization without reliance on electric power, enhancing accessibility and reducing cost.

enhancing accessibility and reducing cost. Participants will be randomly assigned to either the control group, which will receive conventional occupational therapy alone, or the experimental group, which will receive a combination of device-assisted bilateral upper limb training and standard occupational therapy. For the experimental group, the rehabilitation protocol consists of: (1) isolated joint training for the shoulder and elbow, and (2) combined joint training involving functional tasks using rectangular and triangular trajectories. For both types of training, each task will be performed in 5 sets of 20 repetitions, with a 30-second rest between sets. Training will be administered once daily for 30 minutes, five days per week, over a three-week period, totaling 15 sessions. All participants will continue to receive their usual standard care throughout the trial.

#### **6.2.** Concomitant Therapy

Not Applicable

## 7. Efficacy Assessments

#### **Primary endpoint:**

• Fugl-Meyer Assessment for Upper Extremities (FMA-UE)

## Secondary endpoints:

- Brunnstrom stage
- Spasticity: Modified Ashworth Scale (MAS)
- Usability: System Usability Scale (SUS)
- Test-retest reliability of repeated training sessions
- User satisfaction: Satisfaction questionnaire

## 8. Safety Assessments

Not Applicable

## 9. Adverse event reporting

[name] will report SAEs to the IRB of Chang Gung Medical Foundation according to the Serious Adverse Event Reporting Procedures and Guidelines as posted in the Clinical Trials Resource on the website of Chang Gung Medical Foundation IRB. SAE reports to the IRB should include the following information when calling the Medical Monitor:

- Date and time of the SAE
- Date and time of the SAE report
- Name of reporter
- Call back phone number
- Affiliation/Institution conducting the study
- Protocol number
- Title of protocol
- Description of the SAE, including attribution to drug and expectedness

## 9.1 Definitions and reports of Adverse Events

All adverse events that occur after the informed consent is signed (including run-in) must be recorded on the adverse event CRF (paper and/or electronic) whether or not related to study agent. AE Data Elements including:

- AE reported date
- AE Verbatim Term
- CTCAE Term (v 5.0)
- Event onset date and event ended date
- Severity grade
- Attribution to study agent (relatedness)
- Whether or not the event was reported as a Serious Adverse Event (SAE)
- Action taken with the study agent
- Outcome of the event
- Comments

Identify the adverse event using the NCI Common Terminology Criteria for Adverse Events (CTCAE) version 5.0. The CTCAE provides descriptive terminology and a grading scale for each adverse event listed.

AEs will be assessed according to the CTCAE grade associated with the AE term. AEs that do not have a corresponding CTCAE term will be assessed according to their impact on the participant's ability to perform daily activities as follows:

Grade	Severity	Description
1	Mild	Barely noticeable, does not influence functioning
		Causing no limitations of usual activities
2	Moderate	• Makes participant uncomfortable, influences functioning
		Causing some limitations of usual activities

3	Severe	
 
Severe discomfort, treatment needed
 
Severe and undesirable, causing inability to carry out usual activities
 

4	Life threatening	• Immediate risk of death
		Life threatening or disabling
5	Fatal	Causes death of the participant

The possibility that the adverse event is related to study drug will be classified as one of the following: not related, unlikely, possible, probable, definite.

**DEFINITION of Serious Adverse Events**: ICH Guideline E2A and GCP of Taiwan define serious adverse events as those events, occurring at any dose, which meet any of the following criteria:

- Results in death
- Is life threatening (Note: the term life-threatening refers to an event in which the patient was at risk of death at the time of the event; it does not refer to an event which hypothetically might have caused death if it were more severe).
- Requires inpatient hospitalization or prolongation of existing hospitalization
- Results in persistent or significant disability/incapacity
- Is a congenital abnormality/birth defect
- Events that may not meet these criteria, but which the investigator finds very unusual and/or potentially serious, will also be reported in the same manner.

#### 9.2 Adverse event follow-up

All AEs, including lab abnormalities that in the opinion of the investigator are clinically significant, will be followed according to good medical practices and documented as such. Site staff should send follow-up reports as requested when additional information is available. Additional information should be entered on the IRB of Chang Gung Medical Foundation of SAE form in the appropriate format. Follow-up information should be sent to Chang Gung Medical Foundation IRB as soon as possible according to IRB's Serious Adverse Event Reporting Procedures and Guidelines.

## 10. Criteria for the termination of the trial

(1) Enroll requested number of patients and complete the study(2) Relevant research has been published and could confirmed the hypothesis of this study

# 11. Statistical Considerations

## **11.1 Sample size Determination**

Based on the recommendations by Lewis and Sauro (2009), a minimum of 12 participants per group is considered appropriate for usability testing. In this study, participants will be categorized into four subgroups based on muscle tone classification (MAS < 1 or MAS  $\geq$  1) and treatment allocation (experimental or control group), resulting in a minimum required sample size of 48 (12 participants per subgroup). To account for an anticipated dropout rate of approximately 25%, an additional 12 participants will be recruited, leading to a total target enrollment of 60 stroke patients. In addition, 10 trained healthy participants—including caregivers or family members—will be included for usability assessments and device operation training. The total number of evaluable subjects for the study will therefore be 70.

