## 3.2 Study endpoints:

#### 3.2.1 Primary endpoint:

Fugl-Meyer Assessment for Upper Extremities (FMA-UE)

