#### **3.2.2 Secondary endpoints:**

Brunnstrom stage

Spasticity: Modified Ashworth Scale (MAS)

Usability: System Usability Scale (SUS)

Test-retest reliability of repeated training sessions

User satisfaction: Satisfaction questionnaire

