## **11.2 Planned Statistical methods of analysis**

Continuous variables will be presented as means and standard deviations, while categorical variables will be reported as frequencies and percentages. Independent sample t-tests will be used to compare continuous variables between groups, and Pearson's chi-square test will be used for comparisons of categorical variables. One-way analysis of variance (ANOVA) will be applied to assess differences among the multiple subgroups. All statistical analyses will be conducted using SPSS (Statistical Package for the Social Sciences). A p-value of less than 0.05 will be considered indicative of statistical significance.

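### The required size of 48 (60 enrolled) rests only on a usability minimum for a secondary endpoint; nothing stated supports it for the primary FMA-UE comparison

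*Combined protocol and SAP*

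**What the plan says.** Section 11.1 (Sample size Determination) takes its starting figure from a usability recommendation: "a minimum of 12 participants per group is considered appropriate for usability testing". It crosses two MAS strata with two arms to obtain four subgroups, "resulting in a minimum required sample size of 48". It then inflates: "To account for an anticipated dropout rate of approximately 25%, an additional 12 participants will be recruited", which brings enrolment to 60 stroke patients. Section 4.2 and the Synopsis give the same derivation, again on the ground that "a minimum of 12 participants is appropriate for usability assessments".

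The endpoint lists in the Synopsis and in sections 3.2, 7 and 11.2.1 all name FMA-UE as primary and place SUS among the secondary endpoints. Patients are randomised, and FMA-UE is measured before and after the three weeks of training. On analysis, section 11.2 says "Independent sample t-tests will be used to compare continuous variables between groups", with p below 0.05 taken as significant. Section 11.2.4 adds a decision rule: p below 0.05 goes to the alternative hypothesis and p above 0.05 to the null.

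No section gives a target FMA-UE difference, an SD, a power or a precision for FMA-UE. None describes the FMA-UE comparison as pilot or exploratory.

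**The concern.** A figure presented as the minimum the study requires would normally be tied to the primary endpoint. Here it is tied to a secondary one, so the plan does not say what the randomised FMA-UE comparison can show.

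The practical risk comes from pairing that gap with the rule in section 11.2.4. If the true effect is moderate, a trial of this size will more often than not give p above 0.05, and the plan assigns that result to the null hypothesis. An imprecise result would then be reported as if it showed no effect.

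**Working it through.** **1. The plan's own figure.** Inputs from section 11.1: 12 per subgroup, four subgroups, 25% added.
- 4 × 12 = 48, and 48 × 0.25 = 12, so 48 + 12 = 60. Both figures reproduce, with no FMA-UE quantity involved.
- If 25% of the 60 are lost, 60 × 0.75 = 45 remain. The added 12 cover a loss of 12/60 = 20%. Section 11.4 omits cases with missing data, so about 45 is the evaluable number that the plan's own dropout rate implies.

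**2. What that size gives for FMA-UE.** Assumptions: two-sided alpha of 0.05 (sidedness is not stated); 1:1 allocation (implied by 12 per subgroup); strata pooled; an independent-samples t-test as in section 11.2. Results are in SD units because the documents give no FMA-UE SD. The plan also does not say whether the post-treatment score or the change is compared, so the SD is that of whichever is used.

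- CI half-width = t(0.975; n1 + n2 − 2) × √(1/n1 + 1/n2).
  - 24 v 24: 2.013 × 0.2887 = 0.58 SD.
  - 22 v 23: 2.017 × 0.2982 = 0.60 SD.
  - 30 v 30: 2.002 × 0.2582 = 0.52 SD.
- Power comes from the noncentral t distribution with noncentrality d / √(1/n1 + 1/n2), where d is the true difference in SD units. The detectable difference is the d that gives 80% power.

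| Randomised patients analysed | Detectable at 80% power | Power at 0.3 SD | Power at 0.5 SD | Power at 0.8 SD | 95% CI half-width |
|---|---|---|---|---|---|
| 24 v 24 (stated minimum) | 0.83 SD | 17% | 40% | 77% | 0.58 SD |
| 22 v 23 (60 less 25%) | 0.85 SD | 17% | 37% | 75% | 0.60 SD |
| 30 v 30 (no loss) | 0.74 SD | 21% | 48% | 86% | 0.52 SD |

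Within one MAS stratum at 12 v 12, the detectable difference is 1.20 SD.

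**3. In FMA-UE points.** This needs an assumed SD. At 24 per arm, 0.826 × SD gives 4.1 points for an SD of 5, 8.3 for 10 and 12.4 for 15.

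**4. Against the decision rule.** At 24 per arm and a true difference of 0.5 SD, 100% − 40% = 60% of trials would give p above 0.05 and be assigned to the null. At 45 evaluable the figure is 100% − 37% = 63%.

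**The case against.** The plan hides nothing. The title calls the study a usability analysis, all three sample size passages name usability as the basis, and no power for FMA-UE is claimed anywhere. Sizing on one endpoint while naming another as primary leaves the size unjustified, but the two statements are not incompatible. This stands, and it limits the point to a missing justification and an over-broad description of 48 as the required minimum.

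A reader might infer that 48 is too few. The documents do not support that. They give no target difference or SD, and 48 would be about adequate if the true difference were near 0.8 SD or more. Nor can one say that a significant result would exaggerate the effect, since that depends on the true effect being well below this level.

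A reader might also infer a confirmatory efficacy claim. The plan does not use that word. Section 11.2.1 lists endpoints without assigning tests, and the hypothesis-type tick marks cannot be read in the available text. That FMA-UE will be compared by t-test is a fair inference from sections 11.2 and 11.2.4, not a statement in the plan.

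Finally, the Synopsis and section 4.2 mention retrospective data from 60 further stroke patients. If these served as extra controls (an assumption; 30 v 90), the detectable difference would fall to about 0.60 SD and power at 0.5 SD would rise to 65%. Their role is not specified, however, and they would not be randomised evidence, so they do not change the figures for the randomised comparison.

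**Conclusion.** The point holds in a limited form. The sole stated basis for 48/60 concerns a secondary endpoint, and the plan offers no support for it as the size required for the primary FMA-UE comparison. The randomised comparison has 80% power only for differences of about 0.83 to 0.85 SD, with the 95% CI extending about 0.58 to 0.60 SD either side of the estimate. This rests on a two-sided 0.05 t-test, 1:1 allocation and 45 to 48 evaluable patients.

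The consequence is one of interpretation. Under section 11.2.4, a moderate true effect would often be recorded as none. It does not follow that more patients are needed, or that FMA-UE must lose its primary status.

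**What to change.** - **Section 11.1, section 4.2 and the Synopsis:** say that 48/60 was chosen for usability and was not derived from FMA-UE. Add what it gives for the randomised FMA-UE comparison: 80% power for about 0.83 SD and a 95% CI half-width of about 0.58 SD at 24 per arm, or about 0.85 SD and 0.60 SD at the roughly 45 patients left after 25% dropout. State the assumptions (two-sided 0.05, 1:1, SD units) and that the 60 retrospective patients are not part of this comparison.
- **Sections 11.2.1 and 11.2.4:** report the between-arm FMA-UE difference with its 95% CI, and replace the rule for p above 0.05 with a statement that such a result is not evidence of no effect.

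FMA-UE may remain primary. Making usability primary and FMA-UE exploratory is open to the sponsor. That would be a substantive change to the endpoint hierarchy, and it is not needed to resolve this point.

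The cost is protocol and SAP wording, with no added patients or procedures. The downside is a more modest FMA-UE claim.

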#### 1. **Concomitant Treatments** : Not applicable

**1.** Concomitant Therapy :

**2.** Prohibited Therapy :

1. 2.	Main study Hypothesis : Equality Superiority Non-inferiority
2.	Equivalence Other
2.	
3.	Estimated Sample Size : The planned enrollment for this trial includes 60 stroke patients, with an overall evaluable sample size of 70 individuals. This estimation is based on the recommendation by Lewis and Sauro (2009), who suggest that a minimum of 12 participants is appropriate for usability assessments. In the present study, participants will be categorized into four subgroups based on MAS scores (either <1 or ≥1) and intervention type (experimental or control). To ensure that each subgroup has at least 12 participants, a minimum of 48 participants is required (12 per subgroup). An additional 25% (12 participants) will be recruited to account for potential dropout, bringing the total number of stroke patients to be enrolled to 60. Our center has the capacity to recruit and evaluate all 70 participants. In addition to prospective participants, retrospective data from 60 stroke patients will be included for analysis. Furthermore, a total of 10 individuals—including trained therapists and healthy subjects (such as caregivers or family members who have received prior instruction)— will be included to assess usability and support the study's broader evaluation framework. Efficacy assessment group : Intent-to-treat (ITT) Per-Protocol (PP) Interim analysis : Ves No
5.	Statistical methods :
	Continuous variables will be presented as means with standard deviations, while categorical variables will be expressed as proportions. Independent t-tests will be used to compare continuous variables between groups, and Pearson's chi-square test will be applied for categorical data. One-way analysis of variance (ANOVA) will be employed to assess differences across multiple groups. All statistical analyses will be conducted using the Statistical Package for the Social Sciences (SPSS). A p-value of less than 0.05 will be considered statistically significant.
6.	Handling of Missing Data :
	Only cases with complete datasets will be included in the analysis. Incomplete records will be excluded from statistical evaluation to maintain data integrity.

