#### 11.4 Procedure for accounting for missing, unused and spurious data

The approach to the missing data is to simply omit those cases with the missing data and analyze the remaining data.

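### Section 11.1: at the stated dropout of about 25%, 60 enrolled patients leave 45 completers against a minimum of 48, and the 70 evaluable subjects assume no dropout.

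*Combined protocol and SAP*

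**What the plan says.** Section 11.1 starts from a usability rule of thumb: "a minimum of 12 participants per group is considered appropriate for usability testing". Two muscle-tone strata (MAS below 1, MAS 1 or above) and two arms make four subgroups, "resulting in a minimum required sample size of 48 (12 participants per subgroup" in each case. The allowance for loss follows: "To account for an anticipated dropout rate of approximately 25%, an additional 12 participants will be recruited". With these, the number of patients to enrol becomes 60. Ten non-patient participants are then added, and the section concludes: "The total number of evaluable subjects for the study will therefore be 70".

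The Synopsis (Estimated Sample Size) and section 4.2 use the same 48 + 12 = 60, but describe the 12 as a 25% addition for possible dropout and give no dropout rate. Both set planned enrolment at 60 stroke patients "with an overall evaluable sample size of 70 individuals".

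On missing data, the Synopsis states "Only cases with complete datasets will be included in the analysis", and section 11.4 says the approach is to "simply omit those cases with the missing data and analyze the remaining data".

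**The concern.** There are two problems.

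- **Dropout allowance.** A dropout rate applies to the patients enrolled, whereas the plan has taken 25% of the number it wants to keep. In section 11.1 the 25% rate, the 60 enrolled and the minimum of 48 therefore cannot all hold. The wording there also differs in meaning from the Synopsis and section 4.2, where an addition of 25% to 48 is correct arithmetic and corresponds to a loss of 20%.
- **Evaluable total.** A figure of 70 evaluable is possible only if nobody drops out. Each patient outcome in the schedule of activities (FMA-UE, Brunnstrom stage, MAS, SUS, satisfaction) has a post-treatment assessment. Patients lost to follow-up are withdrawn under section 5.3, and incomplete cases are left out of the analysis.

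The rule of 12 per subgroup is the only basis the plan gives for its sample size. A reader would expect at least 12 analysable patients per subgroup and 70 analysable people overall. The plan's own assumptions deliver fewer of both.

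**Working it through.** **Inputs**

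- Minimum per subgroup: 12; four subgroups; minimum total 48 (section 11.1)
- Anticipated dropout: about 25% (section 11.1)
- Added patients: 12; enrolled patients: 60 (Synopsis, sections 4.2 and 11.1)
- Non-patient participants: 10 (same three places)
- Stated evaluable total: 70 (same three places)

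**Reproducing the plan's figures**

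- Minimum: 4 × 12 = 48
- Addition: 0.25 × 48 = 12
- Enrolment: 48 × (1 + 0.25) = 60, which matches the plan
- Evaluable as stated: 60 + 10 = 70, which matches the plan and contains no loss

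**Dropout applied to those enrolled**

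Completers = enrolled × (1 − d), where d is the dropout rate.

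| Dropout rate | Completers of 60 | Average per subgroup |
|---|---|---|
| 20% | 48 | 12.0 |
| 22% | 46.8 | 11.7 |
| 25% | 45 | 11.25 |
| 30% | 42 | 10.5 |

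- Shortfall at the stated rate: 48 − 45 = 3
- Largest dropout that still leaves 48: 1 − 48/60 = 20%
- For comparison, the enrolment at which 25% dropout leaves 48: 48/0.75 = 64, not 60

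**Evaluable total**, assuming none of the 10 non-patients is lost

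- At 20% dropout: 48 + 10 = 58. The stated 70 is too high by 12 (70/58 = 1.21, or 21%).
- At 25% dropout: 45 + 10 = 55. The stated 70 is too high by 15 (70/55 = 1.27, or 27%).
- For all 60 patients to be evaluable, 60/0.80 = 75 or 60/0.75 = 80 would have to be enrolled.

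**How often the minimum would be met (illustration)**

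This assumes 15 patients enrolled in each subgroup and independent dropout, neither of which the plan states. Binomial probabilities are:

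| Dropout rate | At least 48 of 60 complete | At least 12 of 15 in one subgroup | At least 12 in all four |
|---|---|---|---|
| 25% | 23% | 46% | 0.461⁴ = 5% |
| 20% | 58% | 65% | 0.648⁴ = 18% |

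Even at 20%, the figure of 12 per subgroup is an average and not a floor.

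**The case against.** The strongest case on the other side accepts the arithmetic and disputes its weight.

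- **The gap is small.** It is 3 expected completers, the rate is only approximate, and 12 is a usability rule of thumb not tied to the FMA-UE primary endpoint. No planned test changes between 45 and 48. This stands as a limit on the consequences. It does not reconcile the figures, because any rate above 20% leaves fewer than 48.
- **Section 11.1 may be a loose paraphrase.** The Synopsis and section 4.2 describe an addition of 25%, which fits 20% dropout, and that may be what was meant. It is a fair reading and one of the two remedies adopts it. But section 11.1 is the formal sample-size section, and it calls the 25% a dropout rate.
- **Evaluable may mean people to be assessed.** The plan never defines the term, and the Synopsis and section 4.2 say the centre can recruit and evaluate all 70. That supports the view that 70 is a recruitment count carrying the wrong label. The Synopsis and section 4.2 themselves set planned enrolment apart from the evaluable number, so the label misleads.
- **The 60 retrospective patients are left out of 58 or 55.** They were never part of the 70, since 60 prospective patients plus 10 others already make 70. The replacement totals are like for like.
- **An uneven MAS split could cost a subgroup more than 0.75 of a patient.** This is true, and the plan describes no cap on enrolment by stratum. It is a reason to describe 12 as an average, not a reason to leave the error in place.

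**Conclusion.** The concern holds. At the dropout rate in section 11.1, 60 enrolled patients give 45 expected completers (11.25 per subgroup) against the plan's minimums of 48 and 12. Sixty is enough, on average, only if dropout is 20% or less. The stated 70 evaluable is the number enrolled. The corresponding evaluable total is 58 at 20% dropout or 55 at 25%.

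These totals take dropouts as not evaluable, which follows from the complete-case rule, and assume that none of the 10 non-patients is lost. The per-subgroup averages are the completers divided by four; with an uneven MAS split the smaller subgroups would fall further below 12. The shortfall is modest and affects no power claim, but the plan's only stated justification for its sample size is not met by its own figures, and the evaluable count is wrong in three places.

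**What to change.** In section 11.1, choose one of two statements:

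- **(a)** Sixty enrolled patients allow for dropout of up to 20%, leaving 48 completers, an average of 12 per subgroup.
- **(b)** With 60 enrolled and about 25% dropout, 45 completers are expected, about 11 per subgroup, so the minimum of 12 is not met on average.

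In the Synopsis, section 4.2 and section 11.1:

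- Relabel 70 as the number enrolled: 60 prospective patients plus 10 non-patient participants.
- Give the evaluable total separately as 58 under (a) or 55 under (b), assuming none of the 10 is lost. Say that the retrospective records are not counted in it.
- Use the same dropout wording in all three places.

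Both options change only wording and figures and need no extra patients. Option (a) commits the plan to a lower dropout assumption than section 11.1 now states. Option (b) openly gives up the 12-per-subgroup minimum.
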